4. SELECTION OF SUBJECTS

4.1 Number of Subjects

Recruitment will be stopped after 10 cases of pneumonia to *P. aeruginosa* have been documented in this multicentre study and confirmed by a panel of experts maintained blinded. Based on a 10% occurrence of pneumonia in patients colonized by *P.aeruginosa* in the placebo group, the total number will range between 100 and 200 assessable patients, or between 120 and 240 if applying a 20% dropout rate. The total number of patients recruited will actually depend on the precise % of patients developing pneumonia in the placebo group in each centre and on the degree of clinical efficacy seen in the azithromycin treated group (for more details, see Section 11.5 *Justification for Study Size*).

4.2 Inclusion Criteria

Subjects meeting all of the following criteria will be considered for admission to the study:

- Male and non pregnant female aged 18 to 75 years
- Patients hospitalized in ICU, under mechanically assisted ventilation expected to be mandatory for 3 days or more
- Reasonable survival chance within next few days with an Apache score 10-25 as per Appendix H [Knaus et al 1985]
- Tracheal aspirate found positive to *P. aeruginosa*
- The subject (or a close family member in case of incompetence) understands the procedures, agrees to participate, and is willing to give his written informed consent

Informed consent must be obtained for all subjects before enrollment in the study, by patient or by close family member.

4.3 Exclusion Criteria

Subjects presenting with any of the following will not be included in the study:

- Poor prognosis as judged by Apache II score >25
- Pregnant females
- Grossly under- or overweight (BMI <18 or >29)
- Ongoing therapy with a macrolide (clarithromycin, erythromycin, azithromycin, telithromycin)
- Known allergy to any macrolides
- Proven *P. aeruginosa* pneumonia (with documented CFU>10⁴ in BAL or PBS)
- Ongoing antipseudomonal therapy with a susceptible colonizing strain as proven by antibiogramme*

* A list of recommended antibiotics deprived of antipseudomonal activity is provided in Section 6.2 to facilitate the choice of the investigators and to homogenize antibiotic treatment according to type of infections. For patients on antibiotherapy with activity against pseudomonas prior to study entry, they will be maintained in the screening phase for 48 hrs, pending results of antibiogramme on the colonized strain. If found to be susceptible to the antibiotic used, the patient will be excluded from the study; if found to be resistant, the patient will be included in the study (also see Section 6.2)

- Anticipated short duration of mechanical ventilation (≤ 3 days)
- Known drug interaction which could interfere enough with absorption, metabolism, or excretion and thus could decrease efficacy or raise safety concern despite plasma drug monitoring of concomitant therapy (for examples see Section 6.2)
- Severe hepatic insufficiency (type C i.e. score >10 on Child Pugh scale, Appendix A) [Pugh et al 1973]
- Sick sinus syndrome or known long QT syndrome or $QTc >500$ msec
- Recent donation of blood or participation in another clinical trial within 3 months (Europe) or 1 month (USA)
- Any situation exposing the patient to higher risk or possibly confounding results of the study

Any local or country specific regulations must be respected. Any waiver of the inclusion and exclusion criteria listed above must be approved by the investigator and by the monitor on a case-by-case basis prior to enrolling the subject. This must be documented by both the monitor and the investigator.

No subject will be allowed to enroll in this study more than once if study drug was administered. However a patient may be screened on a 2nd occasion under another screening number if he did not meet all inclusion and exclusion criteria in the first instance.

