Compared to other agents, this antibiotic has unique pharmacokinetic properties, with low serum concentrations but high intracellular concentrations of the host cells such as polymorphonuclear leukocytes (PMNL), monocytes, alveolar macrophages and fibroblasts, rendering azithromycin ideal for treating tissue infection [Schentag and Ballou 1991, Reese and Betts 1996, Rapp 1998, Alvarez-Elcoro and Enzler 1999], and especially lung infections [Baldwin et al 1990, Olsen et al 1996]. The high concentrations measured within PMNL and monocytes without changing their intrinsic migrating and phagocytic properties can even be seen as a targeting tool for delivering high concentrations of drug *in situ*. Steady state is achieved after several days of treatment but remanence of these high tissue concentrations is maintained for days after cessation of therapy, another convenient situation to justify short treatment course while ensuring good patient compliance. Accumulation within *P.aeruginosa* however, albeit *in vitro*, has been shown to be in the $\mu\text{g/mL}$ range, thus far away from MIC [Tateda et al 1996].

Tissue concentrations were measured in a study evaluating the pulmonary pharmacokinetics of azithromycin (12 to 96 hours) after a single 500 mg oral dose in volunteers, giving 48 hours after dosing 3.9 µg/mL in bronchial mucosa, 2.18 µg/mL in epithelial lining fluid (ELF), and 1.56 µg/mL for sputum, 30-fold the serum concentration at the time [Baldwin et al 1990]. This 500 mg oral dose is equivalent to 185 mg administered i.v., assuming a 37% absolute bioavailability [33]. Twelve hours after dosing sputum was 2.9 µg/mL. When administering 500 mg on Day 1 and 250 mg from Day 2 to 5 orally to healthy volunteers before bronchoscopy and BAL, ELF concentrations increased from 0.45 µg/mL on Day 1 (4 hrs) to 3.12 µg/mL on Day 5 (4 hrs) to decrease to 0.61 µg/mL 52 hours after last treatment, with a 58-fold ratio to serum [Olsen et al 1996].

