The pharmacokinetics profile and metabolism after i.v. administration has been well reviewed [Rapp 1998, Garey and Amsden 1999, Ref 33]. After i.v. administration of 500 mg over 1 hour in patients with CAP, a C_{max} of 3.63 µg/mL and a C_{min} of 0.20 µg/mL was achieved in plasma on Day 5. In volunteers treated with the same dose over 5 days, a C_{max} of 1.13 and a C_{min} of 0.18 was measured on Day 5, with an 8% increase in C_{max}, a 3-fold increase in C_{min}, and a 61% increase in AUC vs. Day 1. Terminal serum half-life is ~60 hours but biological half-life lasts for days. Metabolism is very limited with excretion occurring mainly unchanged via the feces, urinary excretion being very minor (6% after oral dose, 14% after i.v. at steady state). Thus no dose adjustment is required for patients with class A and B cirrhosis and in patients with renal insufficiency, a major advantage [Ref.33]. Protein binding in serum is dose dependent in the range seen under human exposure, decreasing from 51 % at 0.02 µg/mL to 7% at 1 mg/mL.

No major drug interactions are noted with theophylline, midazolam, cimetidine or zidovudine, a major advantage over clarithromycin and erythromycin. Care is recommended with associated anticoagulants, ergotamine derivatives, triazolam (decreased clearance). Drugs metabolized by the cytochrome P450 pathway e.g. carbamazepine, cyclosporine, hexobarbital, phenytoin, may have increased serum levels [Rapp 1998, Ref 33].

Clinically, azithromycin is given orally as single dose (500 mg or 1000 mg for GU infections), or as loading dose (500 mg) followed by 2 to 4 maintenance doses (250 mg) for upper respiratory tracts infections, usually 3 days for sinusitis and 5 days for community acquired pneumonia. The iv formulation has been used mainly to initiate therapy in seriously ill patients (250 mg/day or 500 mg/day) before switching to oral therapy, or to treat patients unable to take drug orally, usually for 2 to 5 days over 7-10 days of total treatment [Ref 33, Garey and Amsden 1999]. Higher doses and longer treatment durations have been explored however as described under Section 1.4.

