1.4 Rationale for Study and Dose Selection

Based on the scientific hypothesis exposed above and the preclinical evidence *in vitro* and even *in vivo* with animals infected with mutants, the scientific and medical rationale for this exploratory Proof-of-Concept Phase IIa appears warranted. The mechanism of action is thought to involve blocking of quorum sensing, and not to function over any direct bacteriostatic or bactericidal activity by inhibiting bacterial protein synthesis. The levels obtained albeit *in vitro* [Tateda et al 1996] show a dose and a time dependent intracellular accumulation within *P. aeruginosa*, raising from 0.190 µg/mL at 12 hours, to 0.445 at 24 hours, and to 1.709 at 36 hours when grown on agar with 10 µg/mL azithromycin; although it is expected to significantly accumulate within *P. aeruginosa* cells in clinical situations, the levels achieved should remain markedly lower than the identified MIC of ≥ 128 µg/mL over the 24 hours of treatment. The i.v. route is essential in this intubated patient population and ensures well controlled plasma levels and high tissue concentrations which lead to a sustained bronchial mucous concentration: 2 µg/mL is the target level documented *in vitro* and *in vivo* and it should be maintained for at least 12 hours. A daily dose of 300 mg has been selected for this study for iv administration to ensure achieving this goal; based on a 30-fold ratio sputum to serum [Baldwin et al 1990] and assuming a serum through concentration around 0.12 µg/mL at steady state: the bronchial mucous level should be ~ 4 µg/mL throughout dosing intervals.

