* Except if isolated *P. aeruginosa* strain resistant or if medically indicated

Patients on antibiotherapy with activity against pseudomonas prior to study entry will be maintained in the screening phase for 48 hrs, pending results of the antibiogram on the colonized strain. If found to be susceptible to the antibiotic used, the patient will be excluded from the study; if resistant, the patient will be included in the study. Patients already included in the study but requiring an antibiotic with activity against the colonizing *P.aeruginosa* strain will be maintained in the study. Statistical analysis will be performed in these patients as a subgroup and combined with remaining patients only if the pattern of response between treatments is found to be similar to patients treated with no antibiotics or with antibiotics deprived of antipseudomonal activity.

When suspicion of *P.aeruginosa* pneumonia is raised by the clinical situation, a diagnostic procedure must be performed (BAL, PBS) before an antibiotic with antipseudomonal activity can be given empirically. In the case *P.aeruginosa* pneumonia has been diagnosed (Day x) by quantitative culture, dedicated antibiotherapy to treat *P.aeruginosa* infection is recommended and the patient should be taken out of the study at that stage.

Except for other macrolides no treatment is forbidden during the study as reflected in the inclusion/exclusion criteria. Few clinically significant drug interactions are expected to impact on azithromycin clearance, metabolism or distribution and thus concomitant therapy should not influence the clinical outcome of this study. However it is prudent to monitor plasma concentration of concomitant drug which could be increase, thus leading to toxicity, when administering:

- Drugs such as theophyllin, digoxin, ergotamine, dihydroergotamine, or triazolam
- Compounds metabolized by cytochrome P450 system such as carbamazepine, cyclosporine, hexobarbital or phenytoine
- Drugs known to increase QTc wave such as selected H1-antihistaminics
- During therapy with anticoagulants such as warfarin should be monitored regularly by prothrombin time as performed in this study

Dosages of concomitant drugs should be adapted for the best interest of the patient if required for efficacy and/or safety reasons.

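### The macrolide exclusion stops at ongoing therapy, so a patient who has just finished azithromycin can be randomised to placebo with drug still in the lung

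*Protocol*

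**What the plan says.** Section 4.3 of the protocol lists as an exclusion "Ongoing therapy with a macrolide (clarithromycin, erythromycin, azithromycin, telithromycin"). It gives no look-back period. The same list does set one for participation in another trial (3 months in Europe, 1 month in the USA), and it ends with a general clause: "Any situation exposing the patient to higher risk or possibly confounding results of the study". A patient who fails a first screen may return: "a patient may be screened on a 2nd occasion under another screening number".

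Section 6.2 covers macrolides only while the patient is on study: "Except for other macrolides no treatment is forbidden during the study as reflected in the inclusion/exclusion criteria". Its 48-hour screening hold applies to antipseudomonal antibiotics, not to macrolides.

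On persistence, section 1.3 says that "remanence of these high tissue concentrations is maintained for days after cessation of therapy" and that "Terminal serum half-life is ~60 hours but biological half-life lasts for days". It reports a single 500 mg oral dose as "giving 48 hours after dosing 3.9 µg/mL in bronchial mucosa, 2.18 µg/mL in epithelial lining fluid (ELF"), with sputum at 1.56 µg/mL at the same time. Section 1.4 states the level the trial aims for: "2 µg/mL is the target level documented *in vitro* and *in vivo* and it should be maintained for at least 12 hours".

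**The concern.** The study drug is itself a marketed macrolide that the protocol describes as slow to leave lung tissue. The rule asks only whether a macrolide is being given at entry. A patient whose last azithromycin dose was the day before Day 1 is not on ongoing therapy. A patient who fails screening because of a macrolide can be screened again once it is stopped.

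If such a patient is assigned placebo, the first study days are spent with some of the active treatment on board. Two things are at stake:

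- **Primary comparison.** Recruitment stops at 10 confirmed *P. aeruginosa* pneumonias, compared by Fisher's exact test at two-sided 0.10 (sections 4.1 and 11.3), so single events matter. Section 11.2 accepts patients with as few as 3 treatment days before death or 5 before extubation, which overlaps the possible carry-over period.
- **Mechanistic objective.** Autoinducer and virulence measures start on Day -1, 1 and 3 (section 7.1.3), and section 11.3 allows them to be analysed as differences or percentage changes from baseline. Residual drug would lower the baseline in exposed patients of either arm, and the early values in exposed placebo patients.

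**Working it through.** **1. Reproducing the protocol's own exposure figure.** Section 1.3 gives a Day 5 serum trough of 0.20 µg/mL on 500 mg i.v. in pneumonia patients. Scaling to 300 mg gives 0.20 × 300/500 = 0.12 µg/mL, the trough assumed in section 1.4. Applying that section's 30-fold sputum-to-serum ratio gives 30 × 0.12 = 3.6 µg/mL, which matches its stated level of about 4.

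**2. Time at or above 2 µg/mL after the last dose.** I assume log-linear decline.

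- *Sputum, one 500 mg oral dose* (section 1.3: 2.9 at 12 h, 1.56 at 48 h). Half-life = 36 × ln 2 / ln(2.9/1.56) = 40.2 h. Crossing = 12 + 40.2 × log2(2.9/2) = about 34 h.
- *Epithelial lining fluid (ELF), 5-day oral course* (section 1.3: 3.12 at 4 h, 0.61 at 52 h). Half-life = 48 × ln 2 / ln(3.12/0.61) = 20.4 h. Crossing = 4 + 20.4 × log2(3.12/2) = about 17 h.
- *ELF and mucosa, one 500 mg oral dose* (2.18 and 3.9 at 48 h). Both are still above 2 when measured, so at least 48 h.
- *500 mg i.v. daily.* Troughs of 0.18 (volunteers) and 0.20 (patients) × 30 = 5.4 and 6.0 µg/mL, taken as the level 24 h after the last dose. Crossing = 24 + t½ × log2(level/2):

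| t½ | from 5.4 | from 6.0 |
|---|---|---|
| 20.4 h (ELF data above) | 53 h | 56 h |
| 40.2 h (sputum data above) | 82 h | 88 h |
| 60 h (serum, section 1.3) | 110 h | 119 h |
| 69 h (single high i.v. doses, section 1.3) | 123 h | 133 h |

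At 60-69 h the range is 110-133 h, or 4.6-5.6 days. With the shorter half-lives implied by the lung data it is 53-88 h, or 2.2-3.7 days.

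**3. Size of the dilution.** The protocol does not say what share *f* of placebo patients would have had recent azithromycin, so *f* is an assumption. Take the 10% placebo rate of section 11.5 and its complete-protection case (no events on azithromycin). The placebo rate is then 10% × (1 − *f* × *c*), where *c* is the fraction of risk that carry-over removes. With equal arms, the number of assessable patients needed for 10 events is 20 / rate.

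| *f* | *c* = 1 (full protection): rate, N | *c* = 5.6/20 = 0.28: rate, N |
|---|---|---|
| 0% | 10.0%, 200 | 10.0%, 200 |
| 5% | 9.5%, 211 | 9.86%, 203 |
| 10% | 9.0%, 222 | 9.72%, 206 |
| 20% | 8.0%, 250 | 9.44%, 212 |

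The first column is an upper bound. The second assumes protection only for the longest carry-over time, with constant risk over the full 20 treatment days. Shorter stays would raise *c*.

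**4. How much one event matters.** With 100 patients per arm, two-sided Fisher p-values are 0.018 for a 9:1 split of the 10 events, 0.1005 for 8:2 and 0.33 for 7:3. An 8:2 split sits on the 0.10 threshold.

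**The case against.** The general clause in section 4.3 lets an investigator refuse a patient dosed with the study drug the day before, so it would be wrong to infer that such a patient meets every criterion. That stands. But the clause is discretionary, names no drug and no window, and sits beside a criterion that limits itself to ongoing use. It permits exclusion without requiring it.

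Section 6.2 recommends antibiotics for use before or during the study, and its table contains no macrolide. This makes recent exposure less likely but does not bar it.

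The persistence data are mixed. The 2 µg/mL target is stated for bronchial mucous, for which sputum is arguably the closest match, and sputum was already below target at 48 h. ELF was 0.61 µg/mL 52 h after a 5-day oral course. A reader might infer that levels stay above target for days in every lung compartment, and the protocol's figures do not support that. The longest estimate applies a ratio from a single oral dose to an i.v. trough and a serum half-life to lung levels. The ratio step is the one the protocol uses to justify its own dose, but the result remains an extrapolation, largely from volunteers, to ventilated patients.

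Randomisation should balance recent exposure between arms on average, and a carry-over of a few days need not protect for up to 20 days. Both points stand and keep the expected effect small.

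**Conclusion.** The gap is real and modest. The specific criteria admit a patient who has just stopped azithromycin, and the protocol's own data show that such a patient can have lung levels at or above target for between about 17 h and about 5.6 days, depending on the compartment, the previous course and the half-life used.

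The expected consequence is a small dilution of the primary contrast and lowered Day -1 and early mechanistic values in exposed patients. A reader might infer a bias in favour of azithromycin. Nothing in the documents supports that, because the carry-over pulls the comparison towards no difference. The size cannot be fixed, because the share of exposed patients is not given. The rates and patient numbers in the working are illustrations that rest on an assumed share and on no events in the azithromycin arm.

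Nor do the documents support a single interval for all macrolides derived from azithromycin's half-life. Five half-lives at 60-69 h would be 12.5-14.4 days, but the protocol gives no half-life for clarithromycin, erythromycin or telithromycin, and that period is more than twice the longest time above target that its azithromycin figures imply.

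**What to change.** - In section 4.3, extend the criterion from ongoing use to ongoing or recent use. State an azithromycin-free interval before Day 1 that the sponsor justifies against the data in sections 1.3 and 1.4. It should cover at least the longest time above 2 µg/mL that those data imply, about 6 days (5.6 rounded up).
- Justify any interval for other macrolides separately.
- Record prior macrolide use and the date of the last dose on Day -1. The written list in section 7.2.2 names medical history but not prior medication. With the date on file, a sensitivity analysis can leave out any exposed patients.

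The cost is one line in the exclusion criteria, one item on the Day -1 page, and the loss of what should be a small number of recently treated candidates, who say little about azithromycin versus placebo in any case.

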7.2.4. Day x (Day of pneumonia)

The day when a diagnosis of established pneumonia or possible pneumonia is made, will be called Day x. Treatment against *P. aeruginosa* pneumonia will be initiated as soon as the diagnosis is confirmed or if this pathogen is considered as a highly likely cause of pneumonia. The Day x procedures will be implemented as completely as possible on that day (similar to Day n-1) and the remaining items will be performed the next day (Day n). The patient will not receive the test drug on the following morning and the patient will be discharged from the study on Day n with safety and physical examination.

In case of suspicion of pneumonia the necessary explorations will be performed in order to lead to a confirmed diagnosis based on the criteria for *P.aeruginosa* summarized in the table presented below:

Investigation	Documented Pneumonia Day x
BAL	$\geq 10^4$ CFU/mL
Or tracheobronchial aspirate	$\geq 10^5$ CFU/mL
Or protected brush specimen (PBS)	$\geq 10^3$ CFU/mL
CPIS* (see detailed score in App. I)	≥ 6

The diagnosis of pneumonia will be confirmed at later stage under double blind conditions by a panel of independent clinical experts prior to stopping the study to ensure that 10 documented cases of *P. aeruginosa* pneumonia have been included in the study for assessment. The data provided will be patient characteristics, symptoms, all CPIS parameters generated, CPIS overall scores, all X-rays collected and results of BAL (or tracheobronchial aspirate or protected brush). Efforts will be made to achieve a total of 10 pneumonia cases in patients who do not receive concomitant therapy with an antibiotic with activity against the isolated *P. aeruginosa* strain, providing however the overall constraint for a maximum of 240 patients entered will not be trespassed.

Post treatment activities will include:

- Tracheal aspirate 2 (for freezing and transfer to Geneva laboratory for investigation), collected early afternoon (usually 6 hours [if Day x] or 30 hours [if Day n and if applicable] after last test drug administration) if patient still intubated and even if antipseudomonal antibiotherapy has been meanwhile initiated
- ECG, 1 to 4 hours late morning Day x
- Blood pressure, heart rate, respiration rate (early afternoon Day x or Day n)
- Lung X-ray whenever possible that day

- Body temperature (tympanic or rectal) ~17:00
- Local tolerance (up to 24 hours)
- Systemic tolerance (up to 24 hours)

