APPENDIX E

Collection and Assessment of Bronchial Alveolar Lavage (BAL),

Bronchotracheal Aspirate or Protected Brush Specimen (PBS) on Day x

Material

- Sterile fibroscope tip or sterile protected specimen brush
- Sterile catheter
- Sterile saline (0.9 % sodium chloride)
- Special double walled tubes for microbiology 200 mL of adequate size, with screw caps for storage and transport of infectious specimens
- Labels to be printed by Quintiles

Collection of BAL (or bronchotracheal aspirate or PBS)

1. Depending on clinic setup, ICU routine, and patient condition, 3 different techniques may be used on the presumed Day x for confirming diagnosis of pneumonia:
 - Bronchoalveolar lavage (BAL)
 - Bronchotracheal aspirate
 - Protected brush specimen (PBS)
2. A BAL specimen will be taken only if there is strong suspicion of pneumonia to confirm diagnosis (Day x). This procedure should be performed by a trained intense care physician, only if medically not contraindicated, under aseptic conditions and operating as fast as possible to minimize the period when the patient is weaned off from mechanical ventilation. The procedure must be completed fast, using the routine, standardized procedure of the ICU and maintaining as aseptic conditions as possible during aspiration, collection and transfer of BAL specimens to the labeled storage tubes
3. Apply 100% O₂ bagging technique just before shifting the fibroscope or the brush through the tracheal tube
4. The fibroscope tip or brush will be positioned in a segmental ostium (lingual or right middle lobe), the selected side depending on the opacities seen on the lung radiography
5. In case of BAL, 2 aliquots of 50 mL of tepid saline will be infused through the aspiration port and collected via the same port by suction to collect the BAL fluid in 2 sterile tubes:
 - 1 tube will be sent to local laboratory for CFU analysis for diagnostic purposes, centrifugation, and differential cytology
 - 1 tube will be stored at -70 °C pending shipment to Geneva for special analysis (see Section 7.2.3)
6. If the protected brush technique is used, the brush will be disengaged from its sheath when *in situ*, gently sweeping the bronchial wall upon withdrawing. This specimen will be kept for local laboratory assessment. No specimen for the Geneva laboratory will be available using this technique
7. The patient will be put immediately back onto the mechanical ventilation as soon as the procedure is completed

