APPENDIX I

Clinical Pulmonary Infection Score (CPIS)

This Clinical Pulmonary Infection Score (CPIS) has been originally developed by Pugin et al (1991), and later adapted by Singh et al (2000) to diagnose pneumonia on the basis of 7 parameters listed in the table below with the appropriate scoring system (for details on measurements, see Study Schedule on page 10 and Section 7.1.2):

Item	Units	Score 0	Score 1	Score 2
Body temperature	°C	≥36.5 and ≤38.4	≥38.5 and ≤38.9	≥39.0 or ≤36.0
Blood leukocytes	mm ³	≥4'000 and ≤11'000	<4'000 and >11'000	<4'000 and >11'000 and band forms ≥ 50%
Tracheal secretions		Absent	Present Non purulent	Present Purulent
Oxygenation Pa _{o2} /Fi _{o2}	mm Hg	>240 or ARDS*	--	≤240 and no ARDS*
Lung X-ray infiltrate		Absent	Diffuse or patchy	Localized
Progression of lung infiltrate		No progression	--	Progression (after CHF and ARDS excluded)
Tracheal aspirate culture (predominant pathogen)		None or rare or +	Moderate or heavy in culture	Same organism on Gram stain

ARDS = Acute respiratory distress syndrome

Defined as Pa_{o2}/Fi_{o2} ≤200, pulmonary wedge pressure ≤18, and acute pulmonary infiltrates

CHF = Congestive heart failure

Patients with a total CPIS for *Pseudomonas aeruginosa* of:

- <6 are unlikely to have pneumonia
- ≥6 have pneumonia
 - IF BAL ≥10⁴ CFU/mL and possible pneumonia if lower
 - OR if bronchotracheal lavage ≥10⁵ CFU/mL and possible pneumonia if lower
 - OR if protected specimen brush ≥10³ CFU/mL and possible pneumonia if lower

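### The entry exclusion and the primary endpoint define P. aeruginosa pneumonia differently, and no rule requires a counted case to be absent at baseline

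*Protocol*

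**What the plan says.** **Entry.** Section 4.3 excludes proven P. aeruginosa "pneumonia (with documented CFU>10⁴ in BAL or PBS". One cut-off serves both specimens, and neither an aspirate count nor CPIS is mentioned. Section 4.2 requires every patient to have a tracheal aspirate positive for the organism and sets no upper count.

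**Endpoint.** Appendix I treats a CPIS of 6 or more as pneumonia when any one of three culture conditions is met. The lavage condition asks for at least 10⁴ CFU/mL. The bronchotracheal specimen must reach at least 10⁵. The brush has the lowest cut-off of the three: "OR if protected specimen brush ≥10³ CFU/mL and possible pneumonia if lower". The table in section 7.2.4 gives the same three cut-offs and names the second route "Or tracheobronchial aspirate".

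**Timing.** Section 7.2.4: "The day when a diagnosis of established pneumonia or possible pneumonia is made, will be called Day x". It does not say that the condition must have been absent at entry. The expert panel confirms the diagnosis blinded (7.2.4, 11.4). Section 11.2 sets minimum treatment days before death (3) and before extubation (5), and none before pneumonia.

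**Screening data.** Section 7.2.2 collects CPIS, a lung X-ray and a quantitative aspirate count on Day -1. It schedules no BAL or PBS. Appendix E reserves lavage for suspected cases: "A BAL specimen will be taken only if there is strong suspicion of pneumonia to confirm diagnosis (Day x".

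**The concern.** The objective is to prevent or delay pneumonia in colonised patients. A pneumonia already present at randomisation cannot be prevented. If it is counted, it says nothing about prevention but still takes one of the ten places that end recruitment (section 4.1) and enters the Fisher test (section 11.3).

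Two gaps together make this possible. The entry screen is narrower than the endpoint, so the same findings can be acceptable at entry and an event later. And no later step (Day x, the panel review or the analysis population) is instructed to separate prevalent from new cases. With ten events and a test that needs about 8 against 2, one or two such cases can change the conclusion.

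**Working it through.** **Step 1. The two definitions side by side**

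| Element | Exclusion (4.3) | Endpoint (7.2.4, Appendix I) | Gap |
|---|---|---|---|
| BAL | >10⁴ | ≥10⁴ CFU/mL | trivial: exactly 10⁴ only |
| PBS | >10⁴ | ≥10³ CFU/mL | 10-fold |
| Tracheobronchial aspirate | absent | ≥10⁵ CFU/mL | whole route |
| CPIS | absent | ≥6 | not used at entry |

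A patient with CPIS ≥6 and either a PBS count from 10³ to 10⁴ or a tracheobronchial aspirate ≥10⁵ CFU/mL meets the endpoint's numbers but not this exclusion.

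**Step 2. The plan's own figure.** Inputs from section 11.5: 10 cases, 10% placebo rate, equal groups. Total assessable N = 10 / ((0.10 + pA)/2), where pA is the azithromycin rate.
- Complete protection, pA = 0: 10/0.05 = 200.
- No protection, pA = 0.10: 10/0.10 = 100.

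Both stated totals reproduce. They treat all ten cases as new.

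**Step 3. What the test needs.** Two-sided Fisher p-values for ten cases, at 50 and 100 patients per arm:

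| Placebo : azithromycin | 50 per arm | 100 per arm |
|---|---|---|
| 7:3 | 0.318 | 0.331 |
| 8:2 | 0.092 | 0.1005 |
| 9:1 | 0.016 | 0.0185 |

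At the planned 0.10 level, 8:2 is roughly the boundary. It just misses at 100 per arm.

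**Step 4. Illustration with k prevalent cases among the ten.** The documents give no k, so 0 to 4 is an assumed range. Prevalent cases split 50:50 between arms. New cases fall in the placebo arm with probability 1/(1+RR), where RR is the true risk ratio. The placebo count is then Binomial(k, 0.5) + Binomial(10−k, 1/(1+RR)), and the quantity of interest is the probability that it is 8 or more.

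For RR = 0.20, 1/(1+RR) = 0.833:
- k = 0: P(8) + P(9) + P(10) = 0.291 + 0.323 + 0.162 = 0.775 (rounded terms sum to 0.776).
- k = 3: sum over 0, 1, 2, 3 prevalent placebo cases = 0.125×0 + 0.375×0.279 + 0.375×0.670 + 0.125×0.904 = 0.469.

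| True RR | k=0 | k=1 | k=2 | k=3 | k=4 |
|---|---|---|---|---|---|
| 0 | 100% | 100% | 100% | 88% | 69% |
| 0.20 | 78% | 68% | 58% | 47% | 37% |
| 0.50 | 30% | 26% | 22% | 19% | 16% |

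**Step 5. Apparent risk ratio.** Expected placebo cases = k/2 + (10−k)/(1+RR); azithromycin cases are the remainder. For RR = 0.20 and k = 3: 1.5 + 7×0.833 = 7.33 against 2.67, a ratio of 0.36. For k = 1 it is 8.0 against 2.0, or 0.25.

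**The case against.** Several stronger readings are tempting, and the documents do not support them.

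- **That an aspirate-positive patient with a high CPIS can never be excluded.** Section 4.3 also excludes ongoing antipseudomonal therapy when the colonising strain is susceptible, and it has a general clause for situations that could confound the results. Pre-existing pneumonia fits that clause. It is discretionary, however, and would be applied at 20 to 25 sites without a numerical rule.
- **That a Day -1 aspirate count plus CPIS already is the endpoint.** The Day -1 count comes from a routine suction specimen (Appendix D), whereas the Day x specimens are taken to confirm a suspected pneumonia (Appendix E). The introduction says that the organism in lung secretions is not diagnostic, and the endpoint also needs a diagnosis and panel confirmation. So the fair statement is that the numerical criteria can be met, not that an event has occurred. The PBS gap likewise needs a PBS that screening does not schedule.
- **That nobody would notice.** The panel receives all CPIS data and all X-rays, which include the baseline ones. A prevalent case could be seen. But the panel's written task is to confirm the diagnosis, not onset after entry.
- **That power falls to 47%.** This assumes that 3 of the 10 cases were prevalent, for which nothing in the protocol gives support. Under complete protection, one or two prevalent cases leave the chance at 100%.
- **That the trial would favour one arm.** Randomisation balances prevalent cases on average.

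Part of the remedy could sit in a panel charter or in the statistical plan, which is not shown. What stands regardless is the contradiction between 4.3 and the endpoint definition, both fixed in the protocol.

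**Conclusion.** The mismatch holds on the text and does not depend on any calculation. It consists of a 10-fold difference for PBS and the absence of the aspirate route and CPIS from the exclusion. Followed as written, the protocol allows pneumonia present at entry to count toward the primary comparison and the 10-case stop.

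The expected harm is dilution toward no difference and loss of informative events, not false efficacy. Its size is unknown because the number of prevalent cases is unknown. The fall from 78% to between 68% and 37% (1 to 4 prevalent cases, true risk ratio 0.20, even split) shows only how sensitive a ten-event trial is. The sample-size range of 100 to 200 needs no change. Given the partial safeguards and the proof-of-concept purpose, this is a should-fix.

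**What to change.** 1. Reconcile section 4.3 with section 7.2.4 and Appendix I so that entry and endpoint rest on one definition of P. aeruginosa pneumonia. The sponsor decides which specimens and thresholds. The text should also say whether the routine Day -1 aspirate may serve as the aspirate specimen in that definition.
2. Add to sections 7.2.4 and 11.4 that the blinded panel applies the same definition to each case's Day -1 and pre-dose Day 1 record, and that only pneumonia absent at baseline counts toward the primary endpoint and the 10-case stop. The list of data given to the panel should name the Day -1 aspirate count, which it does not do now.

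Cost: a few lines of text, using CPIS, X-ray and culture data already collected. Expect a few more screen failures, or a few cases confirmed but not counted, and so somewhat longer recruitment within the 240-patient ceiling.
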